# 10.2.2 Secondary Endpoint

As a secondary analysis the proportion of subjects with insulin independence at 75 days after transplant will be compared to the proportion of subjects with insulin independence at the University of Pennsylvania in the CIT-07 study using an exact test for two proportions. The same proportion will also be compared to pooled analysis of all subjects in the CIT-07 study from the four CIT centers (see the Statistical Analysis Plan, SAP).

Dichotomous variables such as HbA1c classified as normal ( $\leq$ 7.0%) and non-normal ( $\geq$ 7.0%) will be analyzed in a manner similar to the primary analysis. Continuous variables such as HbA1c, AIRg and c-peptide response will be examined for normality of the distribution and if there is no compelling evidence that the distribution is non-normal, will be analyzed by computing the mean and calculating a 95% confidence interval using the student's t-distribution

If there is compelling evidence that the normal distribution does not apply a logarithmic, square root or other transformation will be done before analyzing the data. An estimate and a 95% confidence interval for each response will be calculated. In addition, the responses will be

compared to the responses in subjects at the University of Pennsylvania in CIT-07 (using an exact test for two proportions, or a t-test, possibly after transformation, for continuous variables).

The additional hypothesis generating endpoints of 3.1.2 and the additional endpoints in 3.1.3 will be analyzed similarly and all the data will be subject to exploratory analysis. For variables that are collected at regular follow up visits, regression models for longitudinal data will be used to examine the responses over time for both dichotomous and continuous variables.

Values will not be imputed for missing secondary endpoints. The frequency of missing data will be reported.

There are a very large number of secondary endpoints. By examining multiple secondary endpoints it is likely that some variables will be found significantly different between the subjects in this study and those from the University of Pennsylvania in CIT-07, but these findings may be Type I errors. Appropriate qualifiers will be reported with any findings which are nominally significant at the 0.05 level or less and such results should be interpreted with extreme caution.

The sample size is small and so confidence intervals will be large and the power to detect differences between the subjects in this study and the subjects in CIT-07 is small.

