### 2.2 Secondary Objectives

The primary and secondary endpoints will be evaluated in this trial. Endpoints will be compared to corresponding endpoints in the CIT07 study.

In addition to achieving insulin independence, we hope to demonstrate that islet transplantation can result in near-normal glycemic control with amelioration from excessive glycemic lability and severe hypoglycemic episodes, and in an improved quality-of-life (QOL). Then the degree and durability of these responses will be determined.

Assessment for progression or development of secondary diabetes complications will include retinal photography, urinary albumin excretion (UAE), and GFR. Finally, we will monitor for procedural complications and AEs related to the immunosuppression regimen.

As previously mentioned, a drawback of the Edmonton approach is the use of CNI agents with known nephrotoxic and diabetogenic side effects. In fact, it's been recognized that some patients transplanted according to the "Edmonton protocol," who have early nephropathy, will experience a deterioration of renal function, mandating discontinuation of tacrolimus. Therefore, the large subset of T1D patients with early nephropathy are currently excluded from clinical islet transplantation trials due to the use of tacrolimus. In this regard, our pre-clinical results in NHP recipients (please see Preclinical Studies) have indicated that combined B- and T- lymphocyte immunotherapy (using a combination of rituximab and Thymoglobulin®), may obviate the need for tacrolimus maintenance therapy. Thus, we will determine the feasibility of a CNI free regimen in human islet transplantation by eliminating the tacrolimus used in the control arm (CIT-07) with the addition of rituximab during the initial induction of immunotherapy in the experimental arm (CIT-05). The benefit or harm of eliminating tacrolimus will be assessed by determining the proportion of subjects who remain insulin-independent at 365 days following the last islet transplant.

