# 5.7.2 Premature Discontinuation of Study Treatment (Transition to "Off-Protocol" Treatment)

Study treatment may be prematurely discontinued for any subject for any of the following reasons:

- 1. The subject is unwilling or unable to comply with the protocol.
- 2. The investigator believes that the study treatment is no longer in the best interest of the subject.
- 3. Graft Failure: Islet allograft failure will be defined as absence of insulin production by transplanted islets, as evidenced by absence of c-peptide. This will be determined by (1) undetectable c-peptide on random testing, followed by (2) undetectable c-peptide at baseline, and at 60 and 90 minutes after MMTT. C-peptide levels obtained in the course of the MMTT will be run at the core lab in Seattle, WA. All study treatment will be tapered and discontinued, at the discretion of the site Principal Investigator, when it is determined that graft failure has occurred.
- 4. An unexpected related SAE. The agent(s) to which the event is attributed will be discontinued.

Subjects who prematurely discontinue study treatment will remain in the study until normal termination, for the purpose of monitoring safety and efficacy parameters and will enter the reduced follow-up schedule outlined in Appendix 2. Data from these subjects will be used in the intent-to-treat analysis. These subjects are permitted to simultaneously enroll in a CIT or site-specific graft failure follow-up protocol, if available.

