The option of a **third islet transplant** under this protocol will be considered only if all of the following conditions are met:

- 1. The subject received greater than 4,000 IE/kg with the second transplant, but remains dependent on insulin for longer than one month after the second transplant.
- 2. There is evidence of partial graft function.
- 3. The CIT PIs, Site PIs, and the Steering Committee have determined that there were no relevant protocol deviations at the site.
- 4. The subject has been compliant with study monitoring and prescribed immunosuppressive therapy.
- 5. No evidence of a serious and life-threatening infection, AE, or other condition that precludes attempting an intraportal injection or continuation of the post-transplant treatment regimen.
- 6. No evidence of PTLD.
- 7. No evidence of progressive renal dysfunction, with blood creatinine rising above 2.0 mg/dL (177  $\mu$ mol/L).
- 8. No evidence of hypersensitization, allergic responses, or other potentially serious drug reactions to medications required by the protocol.
- 9. No evidence of abnormal liver ultrasound and LFTs within 1.5 times the ULN range.
- 10. PRA <50 by flow cytometry (assessment performed locally) and the alloantibody specificity not cross-reactive with antigen(s) present in the subsequent islet preparation in order to avoid unacceptable antigen(s).

Subjects who have completed 8 months of follow-up post-first transplant will no longer be eligible for additional islet transplants funded under this protocol. Subjects that do not meet the criteria for a subsequent transplant and do not have a functioning graft will enter a reduced follow-up schedule (Appendix 2).

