#### REDUCED FOLLOW-UP SCHEDULE

Complete the following assessments at the intervals (+/-7 days) indicated below relative to the day the subject discontinued study treatment. Continue conducting these assessments at the defined intervals until the subject reaches one year post **last** transplant.

- Assess SAEs and hypoglycemic events: q1 month. If subject does not come to the study site for the visit, attempt to obtain information via a phone contact.
- Alloantibody (central lab): q 1 month for the first 3 months and q 3 months thereafter.

Complete the following assessments at 1 year (+/- 14 days) post **initial** transplant:

- Assess SAEs and hypoglycemic events
- Alloantibody (central lab)
- HbA1c (central lab)
- 90 minute c-peptide post MMTT (central lab)
- Serum creatinine (central lab)
- QOL questionnaire (via mail or in-person)

Complete the following assessments at 1 year (+/- 7 days) post **last** transplant:

- Assess SAEs and hypoglycemic events
- QOL questionnaire (via mail or in-person)

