<sup>1 These visits are performed locally but can be done on site if preferred.

<sup>2 Only collect if screening is ≥ 90 days since final parent study visit. Otherwise, results from final parent study visit should be used for screening (Visit 0).

<sup>3 Also collect AE assessment at time of premature study termination, if applicable.

<sup>4 Subjects must record insulin usage for 7 consecutive days within the visit window.

<sup>5 Also collect as clinically indicated.

<sup>6 Chemistry includes: Sodium, albumin, magnesium, chloride, potassium, alk phosphatase, total bilirubin, CO2, creatinine, ALT (SGPT), BUN, gamma GT, glucose, AST (SGOT), calcium, phosphorus

<sup>7 Do not collect after confirmed graft failure.

<sup>8 For those subjects who missed CIMT collection at the 5-year time point, collect at the next available opportunity.

<sup>9 These visits are performed locally but can be done on site if preferred.

 Please refer to CIT07 Protocol Appendix 6 for details on the University of Pennsylvania Sub-Study.

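### Appendix 2 stops most day-365 function measures after treatment stop or graft loss, and Section 10.2.2 bars imputation, so one-year results are selective and insulin independence after the last transplant has no complete scoring rule

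*Protocol*

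**What the plan says.** Section 5.7.2 lists four reasons for stopping study treatment: non-compliance, investigator judgement, graft failure and an unexpected related SAE. It says that these subjects "will enter the reduced follow-up schedule outlined in Appendix 2. Data from these subjects will be used in the intent-to-treat analysis". Section 7.5.1 adds a second route. Subjects who cannot be re-transplanted and "do not have a functioning graft will enter a reduced follow-up schedule (Appendix 2)".

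Appendix 2 has two one-year visits. After the initial transplant it lists SAEs and hypoglycemic events, alloantibody, HbA1c, "90 minute c-peptide post MMTT (central lab)", serum creatinine and QOL. After the last transplant it says "Complete the following assessments at 1 year (+/- 7 days) post last transplant", and the list under that line is SAEs and hypoglycemic events, and QOL.

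Section 10.2.2 gives the rule for all secondary endpoints: "Values will not be imputed for missing secondary endpoints. The frequency of missing data will be reported". Section 10.2.1 has a different rule for the primary endpoint. Death and withdrawal are failures, and any other missing evaluation is a failure unless a later one exists before re-transplantation.

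Sections 4.3.1, 5.7.2 and 10.1 commit to intention-to-treat analysis, and 10.1 puts every transplanted subject in the final analysis. Section 2.2 gives one of the affected endpoints special weight: "The benefit or harm of eliminating tacrolimus will be assessed by determining the proportion of subjects who remain insulin-independent at 365 days", counted from the last transplant.

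The bundled extended follow-up protocol (CIT-08) attaches this footnote to HbA1c, MMTT and central creatinine in its Appendix 1: "Do not collect after confirmed graft failure". Its Section 10.1.2 reports population means of HbA1c and creatinine at each follow-up visit.

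**The concern.** Entry to the reduced schedule is triggered by a poor course: graft loss, toxicity or non-adherence. The schedule then omits the data that the day-365 endpoints need, and the analysis section forbids filling them in. Missingness is therefore tied to outcome. Means of AIRglu, disposition index, CGMS variability, MAGE, LI, Clarke and HYPO would come mainly from subjects doing well enough to stay on treatment.

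The gap is widest at one year after the last transplant. That is the time point Section 2.2 uses to decide whether doing without tacrolimus helped or harmed. With 12 subjects, the handling of two or three people can change the message.

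**Working it through.** **1. Data against need.** For a subject on the reduced schedule:

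| Item | 1 year after initial | 1 year after last |
|---|---|---|
| Insulin use | no | no |
| Capillary, fasting or 90-minute glucose | no | no |
| HbA1c | yes | no |
| 90-minute C-peptide | yes | no |
| Creatinine | yes | no |
| FSIGT, CGMS, MAGE, LI, Clarke, HYPO | no | no |
| SAEs, hypoglycemic events, QOL | yes | yes |

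For a subject with one transplant the two visits coincide and the left column applies. For a re-transplanted subject the right column governs the final-transplant endpoints. The beta-score needs insulin requirements and fasting glucose, and the C-peptide ratio needs fasting glucose and fasting C-peptide. Neither can be calculated at either visit.

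**2. Can insulin independence at day 365 be scored?** Section 3.1 requires being off insulin, plus criteria on HbA1c, capillary glucose, fasting serum glucose and C-peptide (at least 0.5 ng/mL).

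- *Confirmed graft failure.* Section 5.7.2 defines it as undetectable C-peptide on random testing, then at 0, 60 and 90 minutes of the MMTT. That is incompatible with at least 0.5 ng/mL. The answer is a known no, and nothing is imputed.
- *Treatment stopped for another reason.* The graft may still work. Insulin use and glucose are not collected, so independence cannot be confirmed. After a second or third transplant, HbA1c and C-peptide are missing too.
- *Death or withdrawal.* Section 10.2.1 makes these failures at day 75. Nothing equivalent is stated for day 365. Section 10.2.2 analyses dichotomous variables in a manner similar to the primary analysis, which could be read as carrying that rule over, but the same section bars imputation. Two analysts could choose different denominators.

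**3. The plan's own figure.** Section 10.4 gives 0.21 to 0.79 for 6 of 12. The exact (Clopper-Pearson) limits are the 2.5% quantile of Beta(x, n−x+1) and the 97.5% quantile of Beta(x+1, n−x). With x = 6 and n = 12 they are 0.211 and 0.789, which agrees.

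**4. Effect of dropping subjects.** Inputs are n = 12 (Section 10.4) and x = 5 independent at one year (illustrative). The number dropped, f, is not given in the documents and is assumed to be 2 or 4. The reported rate is x/(n−f).

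| f | Rate | Exact 95% CI |
|---|---|---|
| 0 | 5/12 = 42% | 0.152 to 0.723 |
| 2 | 5/10 = 50% | 0.187 to 0.813 |
| 4 | 5/8 = 63% | 0.245 to 0.915 |

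The rate is multiplied by n/(n−f): 12/10 = 1.2 or 12/8 = 1.5. This is an overstatement if the dropped subjects were in truth not independent. Where status is unknown, the honest statement is a range. With two unknown, the rate lies between 5/12 = 42% and 7/12 = 58%.

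**The case against.** The strongest reply is that no passage removes failed grafts from the denominator. Confirmed failure settles the endpoint by definition, and Section 10.1 requires inclusion. This stands. A reader might infer that one-year insulin independence will be calculated only in subjects whose grafts survive; the documents do not say so. If failures are scored from the definition, their contribution to the shift in step 4 is zero.

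It also stands that reduced follow-up does not end all one-year efficacy assessment. The composite of HbA1c and freedom from severe hypoglycemia after the first transplant remains observable, as does stimulated C-peptide at that visit.

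Two further inferences are tempting and unsupported. The illustrative rates could be set against the 40% mark in the synopsis and Section 3, but that mark belongs to 75 ± 5 days, where the failure rule exists. A direction of bias could be claimed for the comparison with CIT-07, but CIT-07's follow-up schedule and scoring are not shown.

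The statistical analysis plan is also not shown and may contain a scoring convention. That answers only part of the point. The no-imputation rule and the Appendix 2 data list are fixed in the protocol, and an analysis plan cannot recover insulin doses that were never recorded.

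In CIT-08, local chemistry (which includes creatinine) and calculated GFR continue after graft failure. The clear loss there is HbA1c.

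**Conclusion.** The point holds for the day-365 function measures and, more narrowly, for insulin independence after the last transplant. Followed as written, Appendix 2 and Section 10.2.2 give selective summaries that do not match the intention-to-treat commitments. The endpoint Section 2.2 relies on cannot be determined for subjects who stopped treatment with a possibly working graft, and it lacks a rule for deaths and withdrawals.

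The illustrated overstatement is 8 points with two non-independent subjects dropped (50 − 42) and 21 points with four (62.5 − 41.7 = 20.8). It rests on the assumed numbers dropped, on 5 of 12 being independent, and on the dropped subjects not being independent. These are secondary endpoints in a 12-subject pilot with wide intervals, and the primary endpoint is not affected.

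**What to change.** 1. **Section 10.2.2.** Extend the 10.2.1 rule to day-365 insulin independence. The denominator is all transplanted subjects. Confirmed graft failure, death and withdrawal count as not independent. After confirmed graft failure, C-peptide is scored as undetectable and beta-score as 0, which Section 9.1.2.6 already equates with no graft function.
2. **Appendix 2.** Record current daily insulin dose at the existing monthly contact and take HbA1c at one year after the last transplant. Subjects who stopped treatment with a working graft are then scored on data and not assumed to be failures. Anyone reporting no insulin still needs the other Section 3.1 criteria checked; if they are not, report the status as undetermined and show the rate both ways.
3. **Other continuous measures.** Report FSIGT, CGMS, MAGE, LI, Clarke and HYPO as conditional on continued full follow-up, with the number excluded for graft failure or treatment stop.
4. **CIT-08.** Keep the annual HbA1c after graft failure, or label the reported means as limited to subjects with functioning grafts.

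The cost is a paragraph of wording, one question at a contact that already occurs, and one blood sample. The sample may need a visit, because Appendix 2 allows the monthly safety contact by phone and QOL by mail. The reported one-year rate may be lower.

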# 10.3 Patient and Demographic Data

# 10.3.1 Baseline Characteristics and Demographics

Summary descriptive statistics for baseline and demographic characteristics will be provided for all enrolled subjects in the ITT sample. Demographic data will include age, sex, race, ethnicity, sex, height and body weight; these data will be presented in the following manner:

- Continuous data (*i.e.*, age, body weight, and height) will be summarized descriptively by mean, standard deviation, median, and range;
- Categorical data (*i.e.*, sex and race) will be presented as enumerations and percentages.

Statistical presentation for baseline and demographic characteristics may be further summarized by values of important baseline predictors of outcome and will be further defined in the SAP.

# 10.3.2 Medical History

Medical history will be collected, including the existence of current signs and symptoms and clinical significance for each body system.

## 10.3.3 Use of Medications

All medications used will be coded using the World Health Organization (WHO) drug dictionary. The number and percentage of subjects receiving concomitant medications or therapies will be presented. Statistical presentation of concomitant medications or therapies may

be further summarized by withdrawal status, favorable outcome status at one year, and other characteristics to be determined by the study investigators.

The percent of subjects who complete the study, losses to follow-up, times to lost to follow-up, and reasons for loss to follow up (*e.g.*, AEs) will be presented. Statistical presentation of study completion may be further summarized by demographic variables and baseline predictors of outcome and will be further defined in the statistical analysis plan SAP.

# 10.5 Interim Analyses to Ensure Patient Safety

The DSMB will be convened to review safety and efficacy data following NIH policy. Formal interim analyses will include distributions of endpoints, biomarkers and AEs.

Because this is a small study and because it is important to collect as much safety data as possible, it is not likely that the DSMB or the investigators will recommend stopping early for evidence of efficacy. The monitoring plan will therefore recommend early stopping only if there is sufficient evidence to conclude that the investigational treatment in either arm is harmful or not effective. Because there is no appropriate historical control rate with which to compare

outcomes in this study, effectiveness will be measured by comparing the subjects in this study to those concurrently enrolled in CIT-07 at The University of Pennsylvania. Should the primary outcome in this study be clearly significantly worse than the primary outcome in subjects in CIT-07 at the same institution, then early termination should be considered.

Because the primary outcome of insulin independence at 75 days after transplant is not necessarily predictive of longer term outcomes, the monitoring boundary will be conservative. It will also be designed to maintain the type I error rate at the final analysis. Interim analyses will be performed after 9 subjects have been enrolled in each group, and also after 10 and 11 subjects have been enrolled in each group. If the unadjusted p-value from the exact one-sided test is less than 0.05 in any of the 3 interim analyses the boundary will be crossed. Because of the discrete distribution of the p-value from the exact test, the probability of early stopping if there is no difference between CIT-05 and CIT-07 is less than 0.05. If the boundary is crossed, the probability of the primary endpoint in CIT-05 is significantly less than the corresponding probability in CIT-07 at the University of Pennsylvania.

In the unlikely event that the boundary is crossed before enrollment is completed the DSMB will be asked for a recommendation on whether to terminate enrollment in the study. If this boundary is crossed the DSMB will also be presented with an analysis comparing the study outcomes to a pooled analysis of all the subjects in CIT-07, not just those at the University of Pennsylvania.

# 10.6 Reporting Deviations from Original Statistical Plan

The principal features of the study design and of the plan for statistical analysis of the data are outlined in this protocol and in the subsequent SAP. Any changes in these principal features will require a protocol or an SAP amendment, which would be subject to review by the Steering Committee, the independent DSMB, the study sponsor, and the health authorities. These changes will be described in the final report as appropriate.

# 11. IDENTIFICATION AND ACCESS TO SOURCE DATA

## 11.1 Identifying Source Data

The investigator is required to keep accurate records to ensure that the conduct of the study is fully documented (see section 12). The results of all clinical and clinical laboratory evaluations will be maintained in the subject's medical records and the data will be transferred to electronic web based CRF's.

Safety data will be recorded electronically in a system specifically designed for this purpose. All data will be reviewed periodically by the DSMB and IRB. The DSMB and/or the IRB have the authority to withdraw any subjects and/or terminate the study because of safety findings.

